**End of Treatment and Follow-up**

Subjects may continue treatment with AG-221 until disease progression or development of unacceptable toxicity. Subjects who experience disease progression per the applicable response criteria ([Section 10.8](#)) who are, in the opinion of the Investigator, benefiting from treatment may be allowed to continue on study drug with approval of the Medical Monitor.

All subjects are to undergo an end of treatment assessment (within approximately 5 days of the last dose of study drug); in addition, a follow-up safety assessment is to be scheduled 28 days after the last dose. Furthermore, all subjects will be followed monthly for disease status, overall survival, and initiation of non-study anti-neoplastic therapy until death, withdrawal of consent, or the end of the study, whichever occurs first.

Subjects who achieve an adequate response to treatment with AG-221 and meet other criteria required to undergo HSCT may proceed to HSCT after discontinuation of study therapy. Those subjects will be followed on study for outcome until disease relapse or end of study to support the overall clinical benefit of AG-221 in this setting.

Subjects who relapse following HSCT may be eligible to restart treatment with AG-221 with Medical Monitor approval and at the discretion of the Investigator, if they have confirmed recurrent IDH2 mutant positive disease, no cancer treatment was administered since the last dose of AG-221 (with the exception of anti-neoplastic therapies used in the course of HSCT such as conditioning regimen or induction-type regimen and anti-GVHD prophylaxis [i.e., methotrexate]), the subject meets the safety parameters listed in the Inclusion/Exclusion criteria, and the trial is open. Subjects will resume AG-221 therapy at the same dose and schedule at the time of discontinuation of study drug.

All subjects are to be followed for survival status follow up every 3 months until death, withdrawal of consent, or end of study for survival. Serious AEs considered related to study drug should continue to be followed until death, withdrawal of consent, or the end of the study as per [Section 11.2](#).

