#### **8.5. Subject Withdrawal Criteria and Replacement of Subjects**

Subjects have the right to withdraw from the study at any time for any reason.

Subjects may withdraw or be withdrawn from study treatment for any of the following reasons:

- Withdrawal of consent
- Experiences unacceptable toxicity
- Any medical condition, which, in the opinion of the Investigators, would put the subject at risk for continuing treatment
- Experiences disease progression (subjects who are, in the opinion of the Investigator, benefiting from treatment may be allowed to continue on study drug with approval of the Medical Monitor)
- Confirmed pregnancy (study therapy should be immediately interrupted based upon a positive urinary human chorionic gonadotropin (hCG), and permanently discontinued if confirmed by a serum  $\beta$ -hCG test)
- Development of an intercurrent medical condition that precludes further participation in the trial
- The Investigator removes the subject from the trial in the best interests of the subject
- Subject requires use of a prohibited concomitant medication ([Section 9.12.3](#))
- Protocol violation: non-adherence to study drug regimen or protocol requirements
- Lost to follow-up
- Death

Discontinuation from study treatment should be considered distinct from discontinuation from the study.

All subjects discontinued from study treatment for any reason should undergo End of Treatment (EOT) procedures, and will have a follow-up visit as described in [Section 10.1](#). All subjects discontinued from study treatment for any reason will be followed further for disease status, overall survival, and initiation of non-study anti-neoplastic therapy until death, withdrawal of consent, or the end of the study, whichever occurs first. Every attempt should be made to collect all data during the follow-up period unless subjects discontinue from the study.

Following discontinuation of study drug, all efforts will be made to complete and report the protocol-defined study observations as completely as possible and to determine the reason for withdrawal.

Once a subject has discontinued study drug (or for a subject in the expansion phase who underwent HSCT post-treatment and has subsequently relapsed and elects not to restart treatment), he or she will enter the follow-up phase for survival.

All subjects are to be followed for survival status follow up every 3 months until death, withdrawal of consent, or end of study for survival.

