**Table 3: Schedule of Assessments: Phase 2**

Visit/Cycle:	Scrn	Cycle 1					Cycle 2			Cycle 3  – Cycle 12		Cycle 13 and beyond 	EOT 	Follow-up	Follow-up HSCT	Survival Follow-up	
		D -28	D1 	D2	D8	D15	D22	D1 	D2	D15	D1						D15
Informed Consent	X																
Review Entry Criteria	X																
Demographics	X																
Medical and Surgical History	X																
Medication History 	X																
Complete Physical Exam	X												X				
Limited Physical Exam		X		X	X		X			X		X					
Height  and Weight	X	X			X		X			X		X	X				
ECOG PS	X	X			X		X			X		X	X	X	X		
Vital Signs 	X				X		X			X			X			X	
Serial Vital Sign 		X															
Single 12-lead ECG 		Please refer to Table 5															
Serial Triplicate 12-lead ECGs 																	
ECHO/MUGA for LVEF	X									X 			X				
Gene Mutation Analysis 	X																
UGT1A1 Gene Testing	X																
Laboratory Evaluations:																	
Hematology 	X	X		X	X	X	X		X	X	X	X	X			X 	
Serum Chemistry 	X	X		X	X	X	X		X	X	X	X	X			X	
Coagulation Studies 	X	X			X		X			X		X	X			X	
Pregnancy Test 	X	X					X			X		X	X				
Bone Marrow Biopsy and Aspirate 	X						X			X		X	X			X 	

Visit/Cycle:	Scrn	Cycle 1					Cycle 2			Cycle 3  – Cycle 12		Cycle 13 and beyond 	EOT 	Follow-up	Follow-up HSCT	Survival Follow-up
Study Day:	D -28	D1 	D2	D8	D15	D22	D1 	D2	D15	D1	D15	D1		28 Days post Discon	Every 28 Days	Every 28 Days
Peripheral blood for molecular and functional studies of plasma, blasts and neutrophils 	X						X			X		X	X		X 	
Evaluate Extent of Disease and Response to Treatment 							X			X		X	X 		X 	
Transfusion Assessment 	X						X			X		X	X 		X 	
Study Drug Administration 		X	X	X	X	X	X	X	X	X	X	X 				
Compliance Assessment 							X			X		X	X			
PK/PD Assessment 		Please refer to Table 5														
Adverse Events	X	X	X	X	X	X	X	X	X	X	X	X 	X	X 		
Concomitant Medications / Procedures	X	X	X	X	X	X	X	X	X	X	X	X 	X	X	X	
Study Completion 														X	X	X

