11. Gene mutation analysis for confirmation of IDH2-mutated disease from a bone marrow sample for subjects in Phase 2 will be based on central laboratory testing performed prior to treatment. A separate tumor (blood and/or bone marrow) sample will be required for central laboratory biomarker analysis (see [Section 10.5](#)). A buccal swab for germ-line mutation analysis will be obtained at screening.
12. Hematocrit, hemoglobin, red blood cell (RBC) count, white blood cell (WBC) count with differential, platelet count, and blast count.
13. If performed, the results and/or samples of hematological assessments, bone marrow biopsies, aspirates, peripheral blood for molecular and functional studies of blasts and neutrophils, and evaluation of the extent of disease and response to treatment will be collected and assessed as part of the study for subjects who undergo HSCT after discontinuation of AG-221. These subjects will be followed at least monthly for assessment of disease response until relapse or end of study.
14. Sodium, potassium, chloride, calcium, magnesium, phosphorus, carbon dioxide (CO2), bicarbonate (HCO3), albumin, total protein, glucose, blood urea nitrogen (BUN), creatinine, uric acid, lactate dehydrogenase (LDH), alkaline phosphatase (ALP), alanine aminotransferase (ALT), aspartate aminotransferase (AST), total bilirubin, direct bilirubin, and indirect bilirubin. In addition, creatine kinase, cardiac troponin, amylase, and lipase are to be obtained at screening, on Day 1 of each treatment cycle, and at the End of Treatment visit.
15. Prothrombin time (PT), activated partial thromboplastin time (aPTT), and international normalized ratio (INR)
16. A serum pregnancy test will be performed at screening (within 7 days prior to first study drug administration) and at the EOT. A urine pregnancy test must be conducted on the day of first study drug administration and confirmed negative prior dosing (Day -3 for subjects undergoing 72-hour PK/PD profile or on C1D1) and Day 1 of all subsequent cycles.

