- Any serious adverse events (SAEs) that are assessed by the Investigator as possibly or probably related to study treatment that occur >28 days post-treatment also are to be reported.
- Subjects who do not go to HSCT are considered to have completed the study at the time of the Day +28 follow-up assessment; subjects who undergo HSCT after discontinuation of AG-221 remain on study until relapse (or end of study). All subjects enter the survival follow-up phase after study completion.
- After the safety follow-up assessments, or for subjects who relapse after HSCT and elect not to restart treatment, subjects are to be contacted every 28 days to assess survival status until death or end of study. All subjects are to be followed for survival status follow up every 3 months until death or end of study.
-  All new anti-neoplastic therapies administered after the last dose of AG-221 are to be captured for all subjects through end of study.
-  Starting at Cycle 13, all assessments may be reduced to every 3 cycles unless otherwise indicated.
-  Starting at Cycle 13, 3 Cycles of AG-221 should be dispensed.
-  Adverse events and concomitant medication must still be captured every 28 days. On cycle Day 1 (every (28 days) when assessments are not performed documented phone contact is acceptable.

**Table 4: Pharmacokinetic and Pharmacodynamic Sampling and Electrocardiogram Schedule for the Phase 1 Dose Escalation and Part 1 Expansion**

Visit/Cycle:	Scrn	Cycle 1												Cycle 2				Cycle 3				Cycle 4 – Cycle 12				F/U			
Study Day:	D -28	D -3 			D1 			D8		D15			D22		D1		D15		D1		D15		D1			EOT	D +28		
Assessment	Blood/ Urine/ ECG	Blood	Urine	ECG	Blood/ Urine/ ECG	Blood	ECG	Blood	ECG	Blood	Urine	ECG	Blood	ECG	Blood	Urine	ECG	Blood	Urine	ECG	Blood	Urine	ECG	Blood	Urine	ECG	Blood	Urine	ECG
Pre-dose 	X 	X	X	X	X	X	X	X		X	X		X		X	X		X	X		X	X		X	X		X	X	
Post-dose																													
Anytime							X			X		X		X		X				X				X	X	X	X	X	X
0.5 hr		X 		X 		X 		X 					X 											X 					
1 hr		X 						X 					X 											X 					
2 hr		X 		X 		X 		X 					X 											X 					

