In the Phase 2 portion of the trial, eligibility, treatment decisions, and response to treatment will be determined by the Investigators based on modified International Working Group (IWG) response criteria (Table 7 and Table 8). Response will also be assessed retrospectively by an Independent Response Adjudication Committee (IRAC). Subjects in the Phase 2 portion of the trial will have the extent of their disease assessed and recorded at screening, on C2D1, every 28 days thereafter through at least Cycle 12 while on study drug treatment, independent of dose-delays and/or dose interruptions, and/or at any time when progression of disease is suspected. An assessment also will be conducted at the End of Treatment visit for subjects who discontinue the study due to reasons other than disease progression. For those subjects who undergo HSCT following discontinuation of AG-221, disease response assessments are to be conducted at least monthly until relapse or end of study.

Starting at Cycle 13, subjects in Phase 2 in remission may have the extent of their disease assessed every 3 cycles (via bone marrow biopsy, aspirates or peripheral blood) unless the local standard of care (SOC) requires more frequent extent of disease assessments. For those subjects

not in remission, it is reasonable to have the extent of their disease assessed every 1 to 2 months to assess for response.

Subjects in the Phase 2 portion of the trial will also be evaluated for RBC and platelet transfusion requirements, including dates of the transfusion and units administered, as well as the associated hemoglobin levels and/or platelet counts, at each disease response assessment.

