10.3.1.4. Duration of Response

Among subjects who have a response of CR, CRi, CRp, PR, or mCR/MLFS by investigator assessment, DOR will be calculated as the date of the first documented response to the date of the first documented disease relapse, progression or death due to any cause, whichever occurs first. Subjects without relapse, progressive disease, or death due to any cause will be censored at the date of the last adequate response assessment.

Table 3: Censoring Rules for Duration of Response

End Date for Duration of Response	Censored (Y,N)	Scenarios
The earliest of death date, relapse date, and progression date	N	A subject has less than 2 consecutive missing response assessments prior to a documented death, relapse, or progression which is before any subsequent anti-cancer therapy.
The last adequate response assessment date before missing assessments	Y	A subject has 2 or more consecutive missing response assessments prior to a documented death, relapse, or progression.
The last adequate assessment date	Y	If a subject did not die, did not relapse or progression, and did not receive any subsequent anti-cancer therapy.
The last adequate assessment date on or prior to the start of subsequent anti-cancer therapy	Y	If a subject did not die, did not relapse or progression on or prior to subsequent anti-cancer therapy.
The last adequate assessment date on or prior to the start of subsequent AML therapy	Y	If a subject died, relapsed, or had disease progression after receiving subsequent anti-cancer therapy.
1) If response assessment after a single documented progressive disease /relapse shows response including CR, CRi, CRp, PR, mCR/MLFS, the relapse/progression before documented response is considered as NE. 2) Subsequent anti-cancer therapy in this table excludes HSCT.		

DOR will be summarized primarily based on investigator assessment. The DOR will be analyzed using KM methods and KM curves. The 25th percentile, median and 75th percentile of the response duration with 2-sided 95% CI will be provided for overall responders in the FAS for Part 1 Expansion, the combined Phase 1, Phase 2, and the combined Phase 1/2 as described in items 2 to 5 of [Section 5.1](#). KM estimates at 3, 6, 9 and 12 months will be provided at individual time points. Due to the limited sample size of each total daily dose group, DOR will not be analyzed for Phase 1 dose escalation.

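### Phase 2 subjects who stop AG-221 without transplant have no scheduled disease assessment after End of Treatment, although the text promises disease-status follow-up, so detection of off-drug relapse for DOR and EFS depends on transplant status or site initiative

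*Protocol*

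**What the plan says.** **The text.** Protocol Section 7.1.4 (End of Treatment and Follow-up) says "all subjects will be followed monthly for disease status, overall survival, and initiation of non-study anti-neoplastic therapy". Section 8.5 says the same without the interval: "All subjects discontinued from study treatment for any reason will be followed further for disease status, overall survival", continuing until death, withdrawal of consent or end of study.

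**The schedule.** In Protocol Table 3 the row "Evaluate Extent of Disease and Response to Treatment" is marked on treatment, at EOT and in the HSCT follow-up column. It is blank in the 28-day Follow-up and Survival Follow-up columns, as are the marrow and peripheral-blood rows. Footnote 26 reads "Subjects who do not go to HSCT are considered to have completed the study at the time of the Day +28 follow-up assessment", after which subjects pass to survival follow-up. Footnotes 3 and 27 describe that phase as a check of survival status, by telephone if wished. Section 9.9.1 lists survival and anti-neoplastic therapy for the monthly contact and omits disease status. SAP Table 10 repeats the schedule.

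**After stopping.** Section 10.8.2, in the same words as 10.8.1, provides one assessment: "An assessment also will be conducted at the End of Treatment visit for subjects who discontinue the study due to reasons other than disease progression". Transplanted subjects get more under Table 3 footnote 13: "These subjects will be followed at least monthly for assessment of disease response until relapse or end of study".

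**The analysis.** SAP 10.3.1.4 says "Subjects without relapse, progressive disease, or death due to any cause will be censored at the date of the last adequate response assessment". SAP 10.3.2.1 applies the same censoring table (SAP Table 3) to EFS. A note to that table excludes HSCT from subsequent anti-cancer therapy, so transplanted subjects keep contributing time to the main DOR analysis.

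**The concern.** Two responders stop the drug on the same day, both in remission. One goes to transplant and is assessed at least monthly until relapse. The other stops for toxicity or by choice and has no further scheduled assessment. If sites work from the schedule, relapse is looked for in the first and not in the second, and the second is censored at EOT.

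That censoring is harmless only if subjects who stop have the same subsequent relapse risk as those who stay on drug. Withdrawal of an active oral agent is a plausible reason for the risk to rise, and without off-drug disease data the trial cannot check it.

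Phase 2 is described as pivotal (Protocol 12.5.7), and that section lists duration of response with the response rates in the primary analysis of clinical activity. The SAP ranks DOR as one of several key secondary endpoints and EFS among the other secondary endpoints. In a single-arm trial, durability is much of what makes a response rate interpretable.

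**Working it through.** **1. Scheduled disease assessment after the last dose, Phase 2**

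| Source | No HSCT | HSCT |
|---|---|---|
| Protocol 7.1.4 | Monthly disease status | Same, and followed to relapse |
| Protocol 8.5 | Disease status, no interval | Same |
| Protocol Table 3 and SAP Table 10 | EOT, then none | EOT, then every 28 days |
| Table 3 footnotes 3, 26, 27 | Complete at Day +28, then survival contact | On study until relapse |
| Protocol 9.9.1 | Survival and new therapy | Followed to relapse |
| Protocol 10.8.2 | EOT | EOT, then at least monthly |

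The blank cells are not an extraction fault, because the footnotes and Section 10.8.2 agree with them. Phase 1 differs: its schedule (Protocol Table 2) appears to include one disease evaluation at the 28-day visit.

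**2. Who is affected.** Relapse (Protocol Table 7) needs marrow blasts, blood blasts or extramedullary disease, which a telephone call cannot establish. Relapse after new non-HSCT therapy is censored anyway (SAP Table 3). The affected group is therefore subjects who stop without relapse, HSCT or new therapy.

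**3. Deaths.** Survival follow-up captures deaths, and death is a DOR and EFS event. But SAP Table 3 censors a death preceded by two or more consecutive missing assessments, and does not say whether months with no scheduled assessment count as missing.

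**4. Number of responders.** The plan's own figure reproduces: the exact 95% interval for 42/125 is 25.4% to 42.6%, and 41/125 has a lower bound of 24.7%, so 42 is the minimum for success. At 15% to 30% stopping, that is 42 × 0.15 = 6.3 to 42 × 0.30 = 12.6 responders.

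**5. Illustration.** The documents give no DOR, stopping share or off-drug hazard, so these are assumptions:
- on-drug event hazard λ = ln 2 / 6 = 0.1155 per month (median 6 months);
- share f stopping before an event without HSCT: 0.15 or 0.30, so the stopping hazard is μ = fλ/(1 − f) = 0.0204 or 0.0495;
- off-drug hazard kλ, with k from 1 to 4.

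With stoppers censored at EOT, Kaplan-Meier estimates exp(−λt), median 6.0 months. With full follow-up,

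S(t) = exp(−(λ+μ)t) + μ[exp(−kλt) − exp(−(λ+μ)t)] / (λ + μ − kλ).

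Solving S(t) = 0.5 gives the full-follow-up median; overstatement = 6/median − 1:

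| k | f = 0.15 | f = 0.30 |
|---|---|---|
| 1 | 6.00 (0%) | 6.00 (0%) |
| 2 | 5.74 (4.6%) | 5.44 (10.4%) |
| 3 | 5.58 (7.6%) | 5.13 (17.0%) |
| 4 | 5.47 (9.6%) | 4.93 (21.7%) |

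Check at f = 0.30, k = 4, t = 4.93: 0.443 + 0.057 = 0.500. The percentages do not depend on the on-drug median; from 9 months, the full-follow-up medians run from 9.0 down to 7.4.

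The model drops every event after EOT, deaths included. It therefore illustrates the case where the schedule is followed literally and later deaths are also censored. EFS was not modelled.

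**The case against.** A reader might infer that off-drug relapse is seen only in transplanted subjects and is otherwise never recorded. The documents do not support that. Sections 7.1.4 and 8.5 are operative text, and 8.5 also asks sites to make every attempt to collect follow-up data. Section 10.7 calls for marrow whenever progression is suspected. Under SAP Table 3 a documented relapse before new therapy, without two consecutive missed assessments, is an event for any subject. What is missing is a scheduled visit, interval or method.

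A reader might also infer that DOR and EFS are biased upward as a matter of fact. They are not shown to be: with k = 1 the bias is zero and only events and precision are lost. No figure in the documents supports any particular k or f.

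Planned sensitivity analyses help in part. Protocol 12.5.7 (DOR and EFS) and SAP 10.3.1.4 (DOR) censor at transplant, which isolates off-drug transplant time. A second SAP analysis counts events despite missed assessments or new therapy, which restores late deaths. Neither can recover a relapse that nobody looked for, and independent adjudication can review only what was collected.

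Timing also counts against a full repair. The latest amendment's justification says the final primary efficacy data are already collected, and SAP 5.1 sets a cut-off of 29 July 2019.

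The narrower point survives: text and schedule disagree, and following the schedule makes relapse ascertainment differ by transplant status.

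**Conclusion.** The inconsistency is established from the documents alone. Non-transplanted Phase 2 subjects have no scheduled disease assessment after EOT, against at least one a month after transplant. For a responder who stops without relapse, HSCT or new therapy, relapse is recorded only through site initiative or a for-cause test. Failing that, DOR and EFS are censored at EOT unless the subject dies, and the treatment of such a death is ambiguous.

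The effect on the estimates is conditional. Under the assumptions above, the overstatement of median DOR runs from 0% (no rise in risk off drug) to about 22% (fourfold hazard, 30% stopping). ORR and its 25% criterion are untouched. This should be corrected, but it does not undermine the primary endpoint.

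**What to change.** **Protocol.** Reconcile Sections 7.1.4, 8.5, 9.9.1 and 10.8.2 with Table 3 and its footnotes 3, 26 and 27, and carry the result into SAP Table 10. Extend footnote 13's collection of tests that happen to be performed to the Follow-up and Survival Follow-up columns, for subjects without relapse or progression at EOT. At each existing contact record relapse status, date and supporting local results until relapse, new anti-leukemic therapy or death.

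**SAP 10.3.1.4 and 10.3.2.1.** Count relapses documented this way as events. State that unscheduled months after EOT are not missing assessments for SAP Table 3, so later deaths count. Report the number of responders censored at EOT by HSCT status.

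**Cost.** A footnote, an eCRF field and SAP text. The contacts already take place, and no new procedure is required. Ascertainment would still depend on local testing: Table 7 asks for a repeat marrow to confirm relapse, which a status reported by telephone cannot supply. Off-drug relapses not collected before the change may not be recoverable. DOR may become slightly shorter. If collection can no longer change, the SAP clarifications and the count by HSCT status are still worth having.
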